9.1.7. Adverse Events Leading to Death

The following TEAE summaries will be generated for the FAS, for each treatment group and overall.

- All TEAEs leading to death (death as an outcome on the eCRF form “Adverse Event” as reported by Investigator), presented by primary SOC and PT, showing the number and percentage of patients with at least 1 TEAE leading to death

9.1.8. Death

The following summaries of deaths will be generated for the FAS, for each treatment group and overall:

- Number and percentage of patients who died during the trial by study period (ie, TEAE period, post-treatment period) and by cause of death
- Number and percentage of non-randomized patients or randomized but not treated patients who died

A listing of all patients who died at any time during the study will be provided.

9.2. Clinical Laboratory Evaluations

The laboratory tests will be performed by the local laboratories according to routine clinical practice at site and country level. The Investigator will review the laboratory report, document this review, and record any clinically relevant findings/changes occurring during the study in the AE section of the CRF.

Additional tests may be performed at any time during the study as determined necessary by the Investigator or required by local regulations; any clinically significant abnormal lab values will be included in the adverse event analyses.

9.2.1. Hematology

Blood for safety laboratory samples will be collected at Screening, Baseline and Weeks 1, 3, 6, 12, and 14. The following parameters will be captured:

- Platelet count
- Red blood cell count
- Hemoglobin
- Hematocrit
- Mean corpuscular volume
- White blood cell count with differential:
 - Neutrophils
 - Lymphocytes
 - Monocytes
 - Eosinophils
 - Basophils

Summary statistics for actual and change from baseline value will be provided by visit and treatment group. The number of subjects with on-treatment CTCAE Grade 3-5 will be summarized for each parameter.

Shift tables between baseline and on-treatment (based on worst-case on-treatment change from baseline) will also be presented for each parameter. Categories will be “low” (define as a value below the normal range), “normal” and “high” (define as a value above the normal range).

Additionally, all relevant data will be listed for the FAS.

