4.4.4. Unscheduled Visits

Unscheduled assessments will not be slotted to a particular time point, but will be used when determining the worst-case value. All unscheduled visits will be included in listings.

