9. SAFETY ANALYSIS

All randomized subjects who received at least one dose of IMP will be included in the safety analysis. All results will be summarized using the FAS by actual treatment group and CVL-871 Combined, which is defined as combined CVL-871 treatment groups.

The observation periods include:

- The pre-treatment period is defined as the time up to first administration of the IMP.
- The on-treatment period is defined as the time from the first administration of the IMP (on Day 1) to the last administration of the IMP + 28 days.
- The post-treatment period is defined as the time from the last administration of the IMP + 29 days to the end of the study follow-up.

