9.2.2. Clinical Chemistry

Clinical chemistry for safety laboratory will be collected at Screening, Baseline and Weeks 1, 3, 6, 12, and 14. Results are to be directly transferred to clinical database (not to be recorded on the eCRFs); any clinically significant abnormality will be captured as an AE.

Clinical chemistry collected parameters will include:

- Blood urea nitrogen
- Creatinine
- Albumin
- Cholesterol (total, HDL-C, LDL-C)
- Triglycerides
- Potassium
- Sodium
- Calcium
- Bicarbonate
- Chloride
- Magnesium
- Glucose
- Aspartate aminotransferase (AST)
- Alanine aminotransferase (ALT)
- Alkaline phosphatase (ALP)
- Gammaglutamyl transferase (GGT)
- Creatine phosphokinase (CPK)
- Total bilirubin and direct bilirubin
- Total protein
- Serum prolactin

Summary statistics for actual and change from baseline value will be provided by visit and treatment group. The number of subjects with on-treatment CTCAE Grade 3-5 will be summarized for each parameter.

Shift tables between baseline and on-treatment (based on worst-case on-treatment change from baseline) will also be presented for each parameter. Categories will be “low” (define as a value below the normal range), “normal” and “high” (define as a value above the normal range). Additionally, all relevant data will be listed for the FAS.

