9.3. Vital Sign Measurements

Vital signs will include systolic and diastolic blood pressures, heart rate, and body temperature. Duplicate blood pressure and heart rate measurements will be obtained sitting/supine (after 5 minutes of rest) followed by a single standing measurement (after 2 minutes of rising from sitting/supine position). The duplicate values (sitting/supine) will be individually recorded, and the values will be averaged by the sponsor for the time point assessment. At each visit, body temperature will be obtained once, at the time of the first blood pressure measurement. Orthostatic blood pressure parameters are calculated as the average measurement in the sitting/supine position minus the measurement in the standing position for the corresponding parameters, for each visit.

Potential clinically significant values and changes of vital signs parameters are:

- Weight: weight gain or loss >7% from baseline
- Systolic blood pressure (sitting/supine average)
 - Max observed value >160 mmHg
 - Max increase from baseline >20 mmHg
 - Min observed value <90 mmHg
 - Greatest decrease from baseline >20 mmHg
- Orthostatic Systolic Blood Pressure
 - Greatest decrease upon standing compared with sitting/supine position ≥ 20 mmHg
 - Max increase upon standing compared with sitting/supine position ≥ 20 mmHg
- Diastolic blood pressure (sitting/supine average)
 - Max observed value >100 mmHg
 - Max increase from baseline >10 mmHg
 - Min observed value <50 mmHg
 - Greatest decrease from baseline <10 mmHg
- Orthostatic Diastolic Blood Pressure

- Greatest decrease upon standing compared with sitting/supine position ≥ 10 mmHg
- Max increase upon standing compared with sitting/supine position ≥ 10 mmHg
- Heart Rate (sitting/supine average)
 - Max observed value > 120 bpm
 - Min observed value < 50 bpm

Vital signs data including changes from baseline will be summarized through descriptive statistics by visit and treatment group. Potential clinically significant values and changes defined above will be summarized based on the maximum/minimum actual post-baseline values and maximum increase/greatest decrease from baseline. Additionally, all relevant data will be listed for the FAS.

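### Laboratory shift tables pick the on-treatment value by an undirected worst-case change but classify it against the normal range, so a mild out-of-range value can be displayed as normal

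*SAP*

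**What the plan says.** SAP 9.2.1 and 9.2.2 use the same rule. In the hematology section the shift is "based on worst-case on-treatment change from baseline"; in the chemistry section the full sentence reads: "Shift tables between baseline and on-treatment (based on worst-case on-treatment change from baseline) will also be presented for each parameter". The three categories are set by the normal range; low, for instance, is "define as a value below the normal range", and high is its mirror image. So one quantity (change) selects the observation and another (value against the range) classifies it. Neither section says in which direction a change is worst, and neither plans separate shifts to the lowest and highest value.

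Blood is "collected at Screening, Baseline and Weeks 1, 3, 6, 12, and 14", which gives five scheduled post-baseline samples. SAP 9 defines the on-treatment period as "the time from the first administration of the IMP (on Day 1) to the last administration of the IMP + 28 days". SAP 4.4.4 adds that unscheduled assessments "will be used when determining the worst-case value"; it speaks of a worst-case value, not a worst-case change, and does not define it either.

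The only other threshold count of laboratory values is for severe grades: "The number of subjects with on-treatment CTCAE Grade 3-5 will be summarized for each parameter". For vital signs, SAP 9.3 works in both directions: potentially clinically significant values and changes "will be summarized based on the maximum/minimum actual post-baseline values and maximum increase/greatest decrease from baseline". For QTcF, SAP 9.5 uses the worst post-baseline value.

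**The concern.** The largest change and the most abnormal value need not be the same observation. A subject whose baseline lies near one limit can cross that limit with a small change and, at another visit, move further in the opposite direction while staying in range. A change-based selector then picks the in-range observation.

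There is a second, separate limitation. Many of the listed parameters can be abnormal in either direction. A table that carries one on-treatment value per subject can show only one of the two, however that value is chosen.

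The shift table is the only planned table that counts subjects with out-of-range values below Grade 3. If its selector is loose, its counts may not mean what a reader will take them to mean.

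**Working it through.** The plan states no figure on this point, so there is nothing to reproduce. The check is of the rule's logic.

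**Inputs from the documents.** There are five scheduled post-baseline samples (Weeks 1, 3, 6, 12 and 14; SAP 9.2.1). The on-treatment window runs to last dose + 28 days (SAP 9). Scheduled dosing runs to Day 84 (Protocol Table 3), so the window extends to 84 + 28 = Day 112. The Week 14 sample is on Day 99 (Protocol Table 1). All five samples are therefore on-treatment for a subject who completes on schedule. The documents give no reference ranges or variances, so those used below are assumptions.

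**Step 1: what a change-based rule selects.** For one subject, change = value − baseline, with baseline fixed. The largest increase is therefore always the maximum value and the largest decrease always the minimum. The largest absolute change is whichever extreme lies further from baseline. The minimum is selected when

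baseline − min > max − baseline, that is, baseline > (max + min)/2,

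and the maximum is selected when the inequality is reversed.

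**Step 2: two examples.**

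- Assumed range 3.5 to 5.1. Baseline 5.0 (normal); on-treatment 5.6 (high) and 4.1 (normal). Changes: 5.6 − 5.0 = +0.6 and 4.1 − 5.0 = −0.9. Midpoint (5.6 + 4.1)/2 = 4.85, which is below 5.0, so 4.1 is selected. The table shows normal to normal and the high value is not shown.
- Assumed range 3.5 to 5.0. Baseline 3.6 (normal); on-treatment 3.6, 3.4, 4.6, 4.0 and 3.8. The largest change is 4.6 − 3.6 = +1.0, an in-range value. The low value, 3.4 − 3.6 = −0.2, is not shown.

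**Step 3: the first example under each reading of worst-case.**

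| Reading | Value shown | Category |
|---|---|---|
| Largest absolute change | 4.1 | normal |
| Largest decrease | 4.1 | normal |
| Largest increase | 5.6 | high |
| Most abnormal value | 5.6 | high |
| Lowest and highest, separately | 4.1 and 5.6 | normal; high |

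A rule fixed in one direction works only when the abnormality lies in that direction. The most-abnormal-value reading never shows an out-of-range subject as normal, but it still shows one direction only if a subject had both a low and a high value. Only the last row covers both.

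**Step 4: illustration of the mechanism.** A simulation used a standard normal parameter, a range of ±1.96 SD, five on-treatment values, within-subject correlation 0.3 to 0.85, no treatment effect and 300,000 subjects. Selection by largest absolute change showed a normal value for 32% to 38% of subjects who had any out-of-range on-treatment value (24% to 26% of those with a normal baseline). Selection by largest decrease alone did so for 45% to 50%. Classifying minimum and maximum separately masked none, as it must. Every input except the five samples is assumed, so these rates show that the mechanism is not confined to contrived cases; they are not estimates for this trial.

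**The case against.** The strongest reply is that the text says worst-case, not largest absolute change. A programmer might take the most abnormal value, the worst categorical shift, or both directions. In the first example few analysts would call a fall from 5.0 to 4.1 the worst case when 5.6 is high. SAP 4.4.4 and 9.5 attach worst to the value, and the table shells, which SAP 1 places in a separate document, may settle the matter. This stands to the extent that a reader cannot infer that the tables will hide abnormal values. But the SAP as written names change as the selector and gives no direction, so the benign reading has to be supplied from outside it.

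A reader might also infer that the primary endpoint is compromised, since it includes clinically significant laboratory changes. The documents do not support that. Clinical significance is judged by the investigator and recorded as an adverse event (Protocol 8.3.4 and Table 10), and SAP 9.2 carries such values into the adverse event analyses. The liver combinations are adverse events of special interest with their own summaries (SAP 9.1.6). Grade 3-5 counts, by-visit summaries (including minimum and maximum, SAP 4.4.5) and listings for the full analysis set remain.

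The vital-signs rule is not a contradiction either. It counts subjects against preset thresholds and is not a baseline-category shift. It shows only that the SAP already summarizes both directions elsewhere.

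**Conclusion.** The point holds as a low-priority correction to the shift tables in SAP 9.2.1 and 9.2.2. It is more than a missing definition: the selector named is a change, while the display classifies values. Read literally, the rule can show an out-of-range subject as normal, and any single selection drops one direction for two-directional parameters.

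What can be lost is mainly an out-of-range value below Grade 3 that is not judged clinically significant, and it is lost from this table only; the listings still hold it. At the planned 25 per arm one misclassified subject is 1/25 = 4 percentage points, and more in a smaller arm, which is relevant because SAP 15 records that the planned size was not reached. That figure is the weight of one subject, not a frequency. No masking rate can be derived from the documents, and the simulated percentages should not be read as one.

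The conclusion that masking can occur rests on worst-case being programmed as the largest change, or as one fixed direction. Under the most-abnormal-value reading only the one-direction limitation remains; if both extremes are tabulated, neither problem does.

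**What to change.** In SAP 9.2.1 and 9.2.2, replace the change-based selector with a value-based one:

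- For parameters of interest in both directions, present two shifts: baseline category to the lowest on-treatment value, and baseline category to the highest.
- For parameters of interest in one direction only (ALT, AST, GGT and CPK are likely candidates), present one shift to the most abnormal value in that direction.
- State which parameters fall in which group.

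Unscheduled values need no new rule, because SAP 4.4.4 already brings them into the worst-case determination.

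The cost is a sentence or two in each section and some extra table blocks. The two sections list 11 hematology and 23 chemistry parameters, so doubling every table would add 34 blocks; the one-direction group reduces that. Prolactin has one scheduled on-treatment sample (Week 12 or early termination), so a second shift would normally repeat the first and can be omitted. Data collection and trial conduct are unaffected.

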9.2.2. Clinical Chemistry

Clinical chemistry for safety laboratory will be collected at Screening, Baseline and Weeks 1, 3, 6, 12, and 14. Results are to be directly transferred to clinical database (not to be recorded on the eCRFs); any clinically significant abnormality will be captured as an AE.

Clinical chemistry collected parameters will include:

- Blood urea nitrogen
- Creatinine
- Albumin
- Cholesterol (total, HDL-C, LDL-C)
- Triglycerides
- Potassium
- Sodium
- Calcium
- Bicarbonate
- Chloride
- Magnesium
- Glucose
- Aspartate aminotransferase (AST)
- Alanine aminotransferase (ALT)
- Alkaline phosphatase (ALP)
- Gammaglutamyl transferase (GGT)
- Creatine phosphokinase (CPK)
- Total bilirubin and direct bilirubin
- Total protein
- Serum prolactin

Summary statistics for actual and change from baseline value will be provided by visit and treatment group. The number of subjects with on-treatment CTCAE Grade 3-5 will be summarized for each parameter.

Shift tables between baseline and on-treatment (based on worst-case on-treatment change from baseline) will also be presented for each parameter. Categories will be “low” (define as a value below the normal range), “normal” and “high” (define as a value above the normal range). Additionally, all relevant data will be listed for the FAS.

9.2.3. Urinalysis

Urine for safety laboratory will be collected at Screening, Baseline and Weeks 1, 3, 6, and 12. Urinalysis results are not to be recorded on the eCRFs; any clinically significant abnormality will be captured as an AE.

Urinalysis collected parameters will include:

- Specific gravity
- Color
- pH, glucose, protein, blood, ketones, bilirubin, urobilinogen, nitrite, leukocyte esterase by dipstick
- Microscopic examination (if blood or protein is abnormal)

All urine laboratory data will be listed for the FAS.

9.3. Vital Sign Measurements

Vital signs will include systolic and diastolic blood pressures, heart rate, and body temperature. Duplicate blood pressure and heart rate measurements will be obtained sitting/supine (after 5 minutes of rest) followed by a single standing measurement (after 2 minutes of rising from sitting/supine position). The duplicate values (sitting/supine) will be individually recorded, and the values will be averaged by the sponsor for the time point assessment. At each visit, body temperature will be obtained once, at the time of the first blood pressure measurement. Orthostatic blood pressure parameters are calculated as the average measurement in the sitting/supine position minus the measurement in the standing position for the corresponding parameters, for each visit.

Potential clinically significant values and changes of vital signs parameters are:

- Weight: weight gain or loss >7% from baseline
- Systolic blood pressure (sitting/supine average)
 - Max observed value >160 mmHg
 - Max increase from baseline >20 mmHg
 - Min observed value <90 mmHg
 - Greatest decrease from baseline >20 mmHg
- Orthostatic Systolic Blood Pressure
 - Greatest decrease upon standing compared with sitting/supine position ≥ 20 mmHg
 - Max increase upon standing compared with sitting/supine position ≥ 20 mmHg
- Diastolic blood pressure (sitting/supine average)
 - Max observed value >100 mmHg
 - Max increase from baseline >10 mmHg
 - Min observed value <50 mmHg
 - Greatest decrease from baseline <10 mmHg
- Orthostatic Diastolic Blood Pressure

- Greatest decrease upon standing compared with sitting/supine position ≥ 10 mmHg
- Max increase upon standing compared with sitting/supine position ≥ 10 mmHg
- Heart Rate (sitting/supine average)
 - Max observed value > 120 bpm
 - Min observed value < 50 bpm

Vital signs data including changes from baseline will be summarized through descriptive statistics by visit and treatment group. Potential clinically significant values and changes defined above will be summarized based on the maximum/minimum actual post-baseline values and maximum increase/greatest decrease from baseline. Additionally, all relevant data will be listed for the FAS.

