2. STUDY OBJECTIVES AND ENDPOINTS

The study objectives and corresponding endpoints are shown in [Table 1](#).

Table 1: Objectives and Endpoints

Objective	Endpoint
Primary	

 To assess the safety and tolerability of 2 fixed doses of CVL-871 in subjects with dementia-related apathy 	
 Incidence and severity of TEAEs Clinically significant changes in ECG results, clinical laboratory evaluations, vital sign measurements, and physical and neurological examination results Clinically significant findings in suicidality assessed using the C-SSRS
Secondary	

 To assess the pharmacodynamic effects of 2 fixed doses of CVL-871 on apathy in subjects with dementia-related apathy 	
 Change from baseline to Visit 5 (Week 6) and Visit 6 (Week 12) in the following: 
 NPI-C apathy domain score NPI apathy domain score DAIR score AES-C score
Exploratory	

 To evaluate the plasma concentrations of CVL-871 in subjects with dementia-related apathy 	
 Plasma concentrations of CVL-871 at Visits 2 (Week 1), 4 (Week 3), 5 (Week 6), and 6 (Week 12)

 To evaluate the effect of CVL-871 neuropsychiatric symptoms other than apathy 	
 NPI-C dysphoria domain score NPI domain scores (other than apathy)

 To assess the effects of 2 fixed doses of CVL-871 on cognition in subjects with dementia-related apathy 	
 Change from baseline to Visit 6 (Week 12) in the ADAS-Cog13 score

 To assess the effects of 2 fixed doses of CVL-871 on functional assessments (eg, activities of basic living, and cognitive, functional, and behavioral performance) in subjects with dementia-related apathy 	
 Change from baseline to Visit 5 (Week 6) and Visit 6 (Week 12) in the following: 
 mADCS-CGIC scores mCGI-S scores CaGI-S scores CaGI-C scores

 Investigate the impact of COMT (Val-Met) status on safety and pharmacodynamics 	
 Evaluation of safety and pharmacodynamic endpoints in subgroups of subjects based on their COMT (Val-Met) status

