4.4.7. Change From Baseline and Percent Change From Baseline

Change from baseline is defined as: Change from baseline = Value at specific time point – Baseline value

Percent change from baseline is defined as:

$$\text{Percent change from baseline}(\%) = \frac{\text{Value at specific timepoint} - \text{Baseline value}}{\text{Baseline value}} \times 100\%$$

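### SAP 9.3 reverses the inequality for a fall in diastolic blood pressure, so the rule flags small or absent falls and omits large ones

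*SAP*

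**What the plan says.** SAP 9.3 (Vital Sign Measurements) sets numeric rules for potentially clinically significant values and changes. The sitting/supine systolic and diastolic blocks have the same four lines in the same order: maximum value, maximum increase, minimum value, greatest decrease. The diastolic block gives the rise as "Max increase from baseline >10 mmHg" and the fall as "Greatest decrease from baseline <10 mmHg". The systolic fall is "Greatest decrease from baseline >20 mmHg".

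The section then commits to tabulating these rules: "Potential clinically significant values and changes defined above will be summarized based on the maximum/minimum actual post-baseline values and maximum increase/greatest decrease from baseline".

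Vital signs are part of the primary safety endpoint, which SAP Table 1 words as "Clinically significant changes in ECG results, clinical laboratory evaluations, vital sign measurements, and physical and neurological examination results". The protocol gives no numeric vital sign change criteria of its own, and SAP section 15 (Changes in the Planned Analysis) says nothing about this line.

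**The concern.** A list of potentially significant changes should flag large changes. This line flags a fall smaller than its cut-off, which includes no fall at all, and excludes the falls that a safety reader would want to see.

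Safety and tolerability are the primary objective, so this row is part of the primary safety reporting. If it is programmed as written, its count is wrong in every arm. The error also works against detection: the more a treatment lowers diastolic pressure, the fewer of its subjects are counted.

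**Working it through.** **Step 1. Compare the change rules in SAP 9.3.**

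| Parameter | Change | Flagged when |
|---|---|---|
| Weight | gain or loss | >7% |
| Systolic, sitting/supine | increase | >20 mmHg |
| Systolic, sitting/supine | decrease | >20 mmHg |
| Orthostatic systolic | decrease or increase | ≥20 mmHg |
| Diastolic, sitting/supine | increase | >10 mmHg |
| **Diastolic, sitting/supine** | **decrease** | **<10 mmHg** |
| Orthostatic diastolic | decrease or increase | ≥10 mmHg |

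The diastolic decrease is the only rule that flags changes below its cut-off. In the systolic block the decrease rule mirrors the increase rule; in the diastolic block it does not.

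**Step 2. Settle the sign convention.** Two readings are possible.

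- *Magnitude:* a fall is a positive number, d = baseline − lowest post-baseline value. The systolic line requires this reading, because a signed change above +20 mmHg would be a rise. The orthostatic definition also makes a fall positive: "Orthostatic blood pressure parameters are calculated as the average measurement in the sitting/supine position minus the measurement in the standing position".
- *Signed:* SAP 4.4.7 defines "Change from baseline = Value at specific time point – Baseline value", so a fall is negative and the line would mean change <10.

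**Step 3. Apply each rule to the subject's lowest change from baseline (mmHg).**

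| Rule | Flagged | Not flagged |
|---|---|---|
| As written, magnitude (d < 10) | +12, +5, 0, −5, −9 | −10, −11, −15, −30 |
| As written, signed (change < 10) | +5, 0, −5, −9, −10, −11, −15, −30 | +12 |
| Reversed (d > 10) | −11, −15, −30 | +12, +5, 0, −5, −9, −10 |

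Under the magnitude reading, the written rule selects the complement of the reversed rule, except that a fall of exactly 10 mmHg is flagged by neither. Under the signed reading, almost every value is flagged. If the author meant a signed change below −10, that selects the same values as the reversed rule.

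**Step 4. Size.** Vital signs are taken at five post-baseline visits (Weeks 1, 3, 6, 12 and 14 in the Schedule of Assessments). The rest is assumed, because the documents give no variability for diastolic pressure: the SD of change, s, is 6, 8 or 10 mmHg, and the mean shift is 0 or −5 mmHg. Baseline and each post-baseline value are independent normals with SD s/√2. Each change then has SD s, and changes at different visits correlate at 0.5 through the shared baseline. With 200,000 simulated subjects per row, the share flagged is:

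| s | Mean shift | d > 10 | As written, magnitude | As written, signed |
|---|---|---|---|---|
| 6 | 0 | 16.0% | 84.0% | 99.8% |
| 6 | −5 | 49.2% | 50.8% | 100.0% |
| 8 | 0 | 30.5% | 69.5% | 99.3% |
| 8 | −5 | 59.0% | 41.0% | 99.9% |
| 10 | 0 | 41.4% | 58.6% | 98.5% |
| 10 | −5 | 64.5% | 35.5% | 99.7% |

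Take placebo with no shift, an active arm shifted by −5 mmHg, and s = 8. The rule d > 10 shows an active-arm excess of 59.0 − 30.5 = 28.5 percentage points. The written rule shows 41.0 − 69.5 = −28.5 points, an apparent benefit. For s = 6 the two differences are +33.2 and −33.2, and for s = 10 they are +23.1 and −23.1.

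**The case against.** No text was found that defends the line, so the case on the other side concerns its consequences.

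- *Other outputs are intact.* The minimum diastolic value rule (<50 mmHg), the systolic decrease rule, both orthostatic rules, the by-visit summaries of change and the listings would still show falls. Protocol 8.3.2 also has clinically relevant vital sign changes recorded as adverse events. This stands: one row is wrong, and the diastolic signal is not lost.
- *Orthostatic hypotension is not affected.* The adverse event of special interest is defined by symptoms, and the orthostatic pressure rules are separate lines with the right direction. This stands. The faulty line concerns sitting/supine change from baseline only.
- *The harm is conditional.* The table shells are in a separate document, and SAP 4.4 calls for double programming, so someone might query the line. That is fair, but two programmers who follow the same specification would reproduce the same error.
- *Under the signed reading no fall is missed.* True, but the row then flags at least 98.5% of subjects in the simulation and separates nothing. The parallel systolic line also rules that reading out.
- *The percentages rest on assumed SDs.* They do, and they only illustrate size. The reversal follows from the SAP's own list.

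**Conclusion.** The line is wrong as written. Under the reading that the parallel systolic line requires, it omits every diastolic fall of 10 mmHg or more and flags every smaller or absent fall. Under the other reading it flags nearly everyone. Neither gives a usable criterion.

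Assuming an SD of change of 6 to 10 mmHg, five post-baseline visits and no drug effect, the row would report 84% to 59% of subjects instead of 16% to 41%, and any difference between arms would change sign. The direction of the error does not depend on those assumptions. The damage is limited to one row, but that row belongs to the primary safety reporting and the published count would be wrong in every arm.

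**What to change.** In SAP 9.3, under sitting/supine diastolic pressure, change the decrease rule from <10 mmHg to >10 mmHg. The cut-off stays the SAP's own, and the direction then matches the diastolic increase and systolic decrease lines. Add a sentence saying that, for these rules, decreases are positive magnitudes (baseline minus post-baseline value), because SAP 4.4.7 uses the opposite sign. Check the table shell and both independent programs against the corrected line.

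The cost is one character, one sentence and one derivation before database lock. If the table has already been produced, rerun it and record the correction in the study report.
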